#### REDUCED FOLLOW-UP SCHEDULE

Complete the following assessments at the intervals (+/-7 days) indicated below relative to the day the subject discontinued study treatment. Continue conducting these assessments at the defined intervals until the subject reaches one year post **last** transplant.

- Assess SAEs and hypoglycemic events: q1 month. If subject does not come to the study site for the visit, attempt to obtain information via a phone contact.
- Alloantibody (central lab): q 1 month for the first 3 months and q 3 months thereafter.

Complete the following assessments at 1 year (+/- 14 days) post **initial** transplant:

- Assess SAEs and hypoglycemic events
- Alloantibody (central lab)
- HbA1c (central lab)
- 90 minute c-peptide post MMTT (central lab)
- Serum creatinine (central lab)
- QOL questionnaire (via mail or in-person)

Complete the following assessments at 1 year (+/- 7 days) post **last** transplant:

- Assess SAEs and hypoglycemic events
- QOL questionnaire (via mail or in-person)

Appendix 3: Sample of Events for Follow-up Protocol

Time Point (months [M] relative to final islet transplant; years [Y] relative to initial transplant)	M15	M18	M21	M24	Y2	M30	M36	Y3	M42	M48	Y4	M54	M60	Y5
Visit Number (relative to final islet transplant)	16	17	18	19		20	21		22	23		24	25	
Visit Window (specified in days)	± 14	± 14	± 14	± 14	± 90	± 30	± 30	± 90	± 30	± 30	± 90	± 30	± 30	± 90
Medical and Diabetes History	X	X	X	X		X	X		X	X		X	X	
Physical Exam	Х	Х	Х	X		X	Х		X	X		X	Х	
Retinopathy Evaluation														X
QOL		Х		Х	Х		Х	X		X	Х		Х	X
AE / Hypoglycemic Events/Toxicity Assessment	Х	Х	Х	X	Х	X	Х	X	Χ	X	Х	X	Х	X
Nutritional assessment		X		X		X	X		X	X		X	X	
CBC (WBC + Diff & Plat)	Х	Х	X	X		X	X		X	X		X	X	
Chemistry (P18 +Mg or P20)	X	X	X	Χ		X	X		Χ	X		X	X	
Lipids		X		X			X			X			X	
Autoantibody 	X	X	Χ	Χ		X	X		Χ	X		X	X	
Alloantibody 	X	X	X	X		X	X		X	X		X	X	
First morning spot urine 		Х		X	Х		Х	X		X	Х		Х	X
GFR					Х			X			Х			X
HbA1c	Χ	X	X	Χ	Χ	Χ	X	X	Χ	Χ	Χ	Χ	X	Χ
Fasting & Post-Prandial Glucose & C-peptide	X	X	X	X	X	X	X	X	X	X	X	X	X	X
MTT	Х	Х	Х	Х		X	Х		Х	X		Х	Х	
Insulin-modified FSIGT				X										
Glycemic Stability (CGMS)	X	X	X	X		X	X		X	X		X	X	
BSR eCRF 	X	X	Х	X	X	X	Х	X	Χ	Χ	Х	Χ	Х	X
MAGE	Х	Х	Х	Х	Х	Х	Х	Х	Х	Χ	Х	X	Х	Х
LI	X	Х	Х	Х	Х	X	Х	X	Χ	X	X	X	X	X
Clarke Score	Х	Х	Х	Х	Х	Х	Х	Х	Х	X	Х	Х	Х	Х
НҮРО	Х	Х	Х	Х	Х	Х	Х	Х	Χ	Х	Х	X	Х	Х
Beta Score	Х	Х	Х	Х	Х	Х	Х	Х	Χ	Χ	Х	X	Х	Х
C-peptide (glucose X creatinine) ratio	Х	Х	Х	Х	Х	Х	Х	Х	Х	X	Х	X	X	X
Sirolimus Levels	Х	X	X	Χ		Χ	X		X	X		X	X	
Tacrolimus Levels	Х	Х	Х	Х		X	Х		X	X		Х	Х	
Serum 	Х	Х	Х	Х		Χ	Х		X	X		X	Х	
PBMC & Plasma 	Х	Х	Х	Х		Х	Х		Х	Х		Х	Х	
RNA 	Х	Х	Х	Х		Χ	Х		Χ	Χ		Χ	Х	

<sup>1Central laboratory assessment

<sup>2First morning spot urine includes: albumin, protein, and creatinine

<sup>3 BSR eCRF is completed using information gathered from subject diary logs, glucometer download data, and insulin requirements.

<sup>4 Archived samples

## **Protocol Synopsis**

**Title** Islet Transplantation in Type 1 Diabetes

Clinical Phase Phase 3

IND Sponsor DAIT/NIAID/NIH

IND Number Exempt

**Activation Date** June 2011

**Accrual Objective** Approximately 75 subjects

Accrual Period N/A

Follow-up Period Varies; the CIT08 follow-up period begins after termination from the CIT

parent study and ends on the final date of the CIT08 study, 01Jul2017.

Study Design A single-arm, multi-center cohort study in islet transplantation

**Treatment Description** Subjects who have received an islet transplant during participation in CIT02,

CIT03, CIT04, CIT05, CIT06, or CIT07 will undergo additional follow-up, including annual assessments of graft function (if applicable) and safety.

**Primary Endpoint** The primary endpoint is duration of sustained **islet allograft function** as

determined by evidence from MMTT of C-peptide production at each anniversary of the final transplant. A C-peptide level greater than or equal to 0.3 ng/mL at 0, 60, or 90 minutes will be considered evidence of islet

allograft function.

**Secondary Endpoints** Secondary endpoints include the following:

• Serum creatinine and calculated eGFR at each annual study visit

- Incidence of serious adverse events during the 12-month period preceding each annual study visit
- Insulin requirements during a one-week period preceding each annual study visit
- Incidence of severe hypoglycemic events during the 12-month period preceding each annual study visit
- HbA1c levels at each annual study visit
- All causes of mortality

Inclusion Criteria

1. Participation in any of the following CIT parent studies: CIT02, CIT03, CIT04, CIT05, CIT06, and CIT07.

- 2. Willingness of participants to continue to use an approved method of contraception during and 4 months after study participation.
- 3. Ability to provide written informed consent.

Exclusion Criteria

1. For female subjects: Positive pregnancy test, presently breast-feeding, or unwillingness to use effective contraceptive measures for the duration of the study and 4 months after discontinuation.

For male subjects: intent to procreate during the duration of the study or within 4 months after discontinuation or unwillingness to use effective measures of contraception. Oral contraceptives, Norplant®, Depo-Provera®, and barrier devices with spermicide are acceptable contraceptive methods; condoms used alone are not acceptable.

- 2. Received an islet transplant in a non-CIT research study.
- 3. Any medical condition that, in the opinion of the investigator, will interfere with safe participation in the trial.

# **Glossary of Abbreviations**

AE Adverse Event

ATG Anti-thymocyte Globulin

BG Blood Glucose

CBC Complete Blood Count

CFR Code of Federal Regulations

cGCP Current Good Clinical Practice

cGMP Current Good Manufacturing Practices

CIT Clinical Islet Transplantation Consortium

CRF Case Report Form

CRO Clinical Research Organization

CTCAE Common Terminology Criteria for Adverse Events

DAIT Division of Allergy, Immunology, and Transplantation

DCC Data Coordinating Center

DCCT Diabetes Control and Complications Trial

DSMB Data Safety Monitoring Board

EC Ethics Committee

FDA Food and Drug Administration

GFR Glomerular Filtration Rate
HbA1c Glycosylated hemoglobin
HLA Histocompatability Antigen

HSV Herpes Simplex Virus

ICH International Conference on Harmonization

IND Investigational New Drug
IRB Institutional Review Board
ITN Immune Tolerance Network

IV Intravenous

MMTT Mixed-Meal Tolerance Test

NIAID National Institute of Allergy and Infectious Disease

NIDDK National Institute of Diabetes and Digestive and Kidney Diseases

NIH National Institutes of Health

PI Principal Investigator

PTLD Post-transplant Lymphoproliferative Disorder

SAE Serious Adverse Event
SAP Statistical Analysis Plan

Page 9 of 39

SOP Standard Operating Procedure

T1D Type 1 Diabetes

TCAE Terminology Criteria for Adverse Events

## **Study Definitions**

**Graft failure:** Islet allograft failure will be defined as absence of insulin production by transplanted islets, as evidenced by C-peptide < 0.3 ng/mL. This will be determined by (1) C-peptide < 0.3 ng/mL on random testing, followed by (2) C-peptide < 0.3 ng/mL at baseline, and at 60 and 90 minutes after MMTT. C-peptide levels obtained in the course of the MMTT will be run at the core lab in Seattle, WA; allow 72 hours for results. Participants with confirmed graft failure do not need to complete subsequent metabolic assessments.

**Islet allograft function:** A C-peptide  $\geq 0.3$  ng/mL at 0, 60, or 90 minutes after MMTT will be considered evidence of insulin production by transplanted islets. C-peptide levels obtained in the course of the MMTT will be run at the core lab in Seattle, WA; allow 72 hours for results.

Parent studies: CIT02, CIT03, CIT04, CIT05, CIT06, and CIT07.

**Severe hypoglycemia:** An event with one of the following symptoms: memory loss; confusion; uncontrollable behavior; irrational behavior; unusual difficulty in awakening; suspected seizure; seizure; loss of consciousness; or visual symptoms, in which the subject was unable to treat him/herself and which was associated with either a blood glucose level < 54 mg/dL [3.0 mmol/L] or prompt recovery after oral carbohydrate, IV glucose, or glucagon administration).

## 1. BACKGROUND AND RATIONALE

## 1.1 Background

The Clinical Islet Transplant Consortium opened in October 2004 under a research initiative (RFA-DK-04-005) sponsored by the National Institute of Diabetes and Digestive and Kidney Diseases (NIDDK) and the National Institute of Allergy and Infectious Diseases (NIAID). This consortium conducts seven trials in islet transplantation, six of which (CIT02, CIT03, CIT04, CIT05, CIT06, and CIT07) will be the source of study subjects in CIT08. Approximately 75 subjects are expected to be enrolled and followed in this trial.

#### 1.2 CIT Parent Studies

The CIT studies aim to determine the safety and efficacy of islet transplantation with the goal of obtaining licensure in the U.S.

**CIT07 (phase III licensure study)**: The primary objective is to demonstrate, in a multicenter, single-arm study, the safety and efficacy of islet transplantation for the treatment of T1D in subjects with hypoglycemia unawareness and a history of severe hypoglycemic episodes.

**CIT06 (phase III licensure study):** The primary objective is to demonstrate that islet transplantation in patients with established kidney transplants leads to improved metabolic control as measured by serial HbA1c levels and a reduced occurrence of hypoglycemic events.

CIT02 (phase II pilot study): The primary objective is to determine the proportion of subjects who are insulin independent at  $75 \pm 5$  days posttransplant after one islet transplant among subjects treated with lisofylline in addition to the standard islet transplant regimen used in the CIT-07 protocol.

**CIT03 (phase II pilot study)**: The primary objective of this protocol is to assess the safety and efficacy of an immunosuppressive regimen consisting of ATG (1st transplant only), basiliximab (subsequent transplants only), etanercept, DSG, sirolimus, and low-dose tacrolimus on posttransplant islet function in subjects with T1D.

CIT04 (phase II pilot study): The primary objective of this protocol is to assess the safety and efficacy of an immunosuppressive medication consisting of a monoclonal antibody IL-2 receptor blocker (daclizumab or basiliximab), belatacept and mycophenolate mofetil in islet transplantation. The primary efficacy measure will be the proportion of insulin-independent subjects at day 75 (± 5 days) following the first islet transplant.

CIT05 (phase II pilot study): The primary objective is to determine the proportion of subjects who are insulin independent at  $75 \pm 5$  days following the first islet transplant among subjects treated with an experimental islet transplant immunosuppression regimen which includes rituximab and excludes tacrolimus.

### 1.3 Rationale for Current Protocol

The purpose of this protocol is to collect long-term follow-up information on the safety and efficacy of islet transplantation in CIT subjects after their completion in their CIT parent study.

## 1.4 Known and Potential Risks and Benefits to Human Subjects

Administration of all immunosuppressive and immunomodulatory therapies used presently to prevent rejection of transplanted tissues carry general risks of opportunistic infection and malignancy, including lymphoma (~1%), and skin cancers. These agents are not recommended for nursing mothers, and it is recommended (and mandated in the current protocol) that women of childbearing potential use effective contraception before, during and for at least 4 months following administration of these agents.

The agents listed below are those currently used in the parent trials. We anticipate that these will be used in CIT08. However, it is possible that this can change due to changes in drug availability.

#### 1.4.1.1 SIROLIMUS (RAPAMUNE®)

The FDA approved sirolimus (rapamycin, Rapamune®) as an immunosuppressive agent in 1999 (see product monograph for details). In 208 kidney transplant recipients receiving 5 mg of sirolimus daily compared to 124 receiving placebo, there was an increased incidence of hypercholesterolemia (46 vs. 23%), hyperlipemia (57 vs. 23%), rash (20 vs. 6%), arthralgia (31 vs. 18%), diarrhea (35 vs. 27%), anemia (33 vs. 21%), leucopenia (13 vs. 8%), thrombocytopenia (30 vs. 9%), and hypokalemia (17 vs. 9%). Side effects are related to drug concentration and are improved with maintenance of the sirolimus 24-hour trough level between 10–20 ng/mL.

Of infections, only mucosal herpes simplex virus (HSV) occurred at a greater rate with sirolimus. There was no increase in rate of malignancy (3.4 vs. 3.1%). While sirolimus was originally proposed as a non-nephrotoxic agent, it is becoming apparent that sirolimus-associated nephrotoxicity does occur in clinical practice. Crew *et al.* described two patients with thrombotic microangiopathy secondary to sirolimus exposure. Sirolimus alters the pharmacokinetic profiles of other CNIs (*e.g.*, tacrolimus) and may thereby potentiate nephrotoxicity. Fervenza *et al.* described nephrotoxicity from sirolimus in patients with chronic glomerulopathies that was non-reversible on cessation of therapy. Nephrotoxicity from combined sirolimus and tacrolimus has been described in patients with T1D undergoing islet transplantation, particularly where there is underlying pre-existing renal damage from diabetes.

The majority of islet transplant recipients receiving sirolimus in conjunction with tacrolimus have experienced transient mouth ulceration and lower extremity edema; perinephric edema and a high incidence of benign ovarian cysts have also been described in islet recipients in association with sirolimus. Pneumonitis and colitis have also occurred. The most common (> 30%) adverse reactions are: oral apthous ulcers, peripheral edema, hypertriglyceridemia, hypertension, hypercholesterolemia, increased creatinine, abdominal pain, diarrhea, headache, fever, urinary tract infection, anemia, nausea, arthralgia, pain, and thrombocytopenia.

Concerns have been raised by the FDA regarding trials of combined sirolimus/tacrolimus in liver transplant recipients, where there has been a statistically increased risk of hepatic artery thrombosis and late death in sirolimus-treated recipients. A careful analysis of these events does not establish causative association between sirolimus/tacrolimus and thrombosis or death events. There was no increased association with portal venous thrombosis in the liver transplant trials. While sirolimus continues to be used off-label in islet recipients, there is not

presently felt to be an association between portal thrombus formation in islet recipients and the use of sirolimus or tacrolimus.

### 1.4.1.2 TACROLIMUS (PROGRAF®)

Tacrolimus (Prograf®, FK506) has been in wide clinical use for the prevention of allograft rejection since 1994 when the FDA approved it after several years of testing. Tacrolimus is a macrolide antibiotic which inhibits calcineurin after binding intracellularly to FKBP12 within T cells, inhibiting IL-2 transcription. Tacrolimus is invariably administered with other immunosuppressive agents but is known to be associated with several side effects including hypertension, diabetes, nephrotoxicity, hyperkalemia, dyslipidemia, pruritis, neurotoxicity, neurologic sequelae (including tremor, ataxia, and extremely rarely central pontine myelinolysis), posterior reversible encephalopathy syndrome (PRES), progressive multifocal leukoencephalopathy (PML), interstitial lung disease, BK nephropathy, nausea, vomiting and diarrhea (see product monograph for details). In 205 kidney transplant recipients receiving tacrolimus, the principal AEs were neurologic (tremor [54%], headache [44%], insomnia [32%], paresthesia [23%]) and gastrointestinal (diarrhea [44%], nausea [38%], constipation [35%]) complaints, hypertension (50%), and kidney dysfunction (52%); hyperkalemia (31%) and hyperglycemia (22% in previous non-diabetics) also occurred. The severity of these events appears to be dose dependent, with very high plasma levels also producing delirium, seizures, and coma. Complications can be minimized with the relatively low dose long-term therapy typically used in islet transplant trials.

## 1.4.1.3 CYCLOSPORINE (NEORAL®)

Cyclosporine is associated with renal dysfunction, tremors, hirsutism, hypertension, and gum hyperplasia.

# 1.4.1.4 MYCOPHENOLATE MOFETIL (CELLCEPT®) AND MYCOPHENOLATE SODIUM (MYFORTIC®)

CellCept® and Myfortic® are associated with: diarrhea, leucopenia, vomiting, and evidence of higher frequency of certain types of infections, some of which can be fatal. CellCept® and Myfortic® may increase the risk of developing lymphoproliferative disease, lymphomas, and other malignancies, particularly of the skin, and have been known to cause fetal harm (congenital malformations and pregnancy loss) when administered to a pregnant woman. Cases of progressive multifocal leukoencephalopathy, sometimes fatal, and pure red cell aplasia have been reported in patients treated with CellCept® or Myfortic® in combination with other immunosuppressive agents.

Contraception requirements are outlined in the eligibility criteria.

## 1.4.2 Risk of Study Procedures

The procedures involved with the care of research subjects undergoing clinical islet transplantation include risks pertaining to: a) blood draw testing, b) metabolic stimulation testing, and c) specific follow-up testing.

#### 1.4.2.1 METABOLIC STIMULATION TESTING

The risks associated with metabolic testing are generally regarded as minor. Placement of IV cannulae may be associated with pain and discomfort at the puncture site, bruising, bleeding, displacement, interstitial infusion of fluids, local vein thrombosis, infection or thrombophlebitis.

The administration of bolus glucose by mouth or intravenously may lead to acute hypoglycemia or hyperglycemia, or rarely may induce ketoacidosis.

#### 1.4.2.2 BLOOD DRAW TESTING

Peripheral blood draws performed during these research studies will not exceed 450 mL per sixweek period. The subject may experience some discomfort at the site of the needle entry, and there is risk of bruising at the site. There is a remote risk of fainting or local infection.

#### 1.4.3 Benefits

The major benefit of this study will be to provide further information on the duration and quality of function of islet grafts beyond the CIT parent study's follow up period.

# 2. OBJECTIVES

# 2.1 Primary Objective

The primary objective is to provide extended follow-up for safety and efficacy and to support continued islet graft function to participants previously enrolled in CIT02, CIT03, CIT04, CIT05, CIT06, or CIT07.

# 3. SELECTION OF SUBJECTS

## 3.1 Inclusion Criteria

Patients who meet all of the following criteria are eligible for participation in the study:

- 1. Participation in any of the following CIT parent studies: CIT02, CIT03, CIT04, CIT05, CIT06, and CIT07.
- 2. Willingness of participants to continue to use an approved method of contraception during and 4 months after study participation.
- 3. Ability to provide written informed consent.

## 3.2 Exclusion Criteria

Patients who meet any of these criteria are not eligible for participation in the study:

- 1. For female subjects: Positive pregnancy test, presently breast-feeding, or unwillingness to use effective contraceptive measures for the duration of the study and 4 months after discontinuation. For male subjects: intent to procreate during the duration of the study or within 4 months after discontinuation or unwillingness to use effective measures of contraception. Oral contraceptives, Norplant®, Depo-Provera®, and barrier devices with spermicide are acceptable contraceptive methods; condoms used alone are not acceptable.
- 2. Received an islet transplant in a non-CIT research study.
- 3. Any medical condition that, in the opinion of the investigator, will interfere with safe participation in the trial.

## 4. STUDY DESIGN

This is an open-label, multi-center cohort study for participants from the CIT02, CIT03, CIT04, CIT05, CIT06, and CIT07 studies who continue to have islet graft function. These participants will continue immunosuppressive medications under CIT08 and will be assessed for islet function on an annual basis.

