## 10. STATISTICAL CONSIDERATIONS AND ANALYTICAL PLAN

## 10.1 Study Endpoint Assessment

## 10.1.1 Primary Endpoint

The primary endpoint is time to islet graft failure. The purpose of the analyses will be to estimate the probability of islet graft failure as a function of time from entry into the study . Life table methods will be used to estimate the survival curve and provide confidence intervals for the probability of islet graft survival for selected time points.

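### CIT08 defines its cohort both with and without a graft-function requirement, so the primary graft-survival curve has no fixed meaning

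*Protocol*

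**What the plan says.** All section numbers here are those of the CIT08 protocol unless CIT05 is named.

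**Who is in the cohort.** Section 4 (Study Design) limits CIT08 to participants "who continue to have islet graft function. These participants will continue immunosuppressive medications under CIT08". Section 3.1 asks only for "Participation in any of the following CIT parent studies: CIT02, CIT03, CIT04, CIT05, CIT06, and CIT07", plus contraception and consent. Section 3.2 has three exclusions: pregnancy and contraception, "Received an islet transplant in a non-CIT research study", and an interfering medical condition. None concerns graft failure. The synopsis covers subjects transplanted in a parent study, who "will undergo additional follow-up, including annual assessments of graft function (if applicable) and safety". Section 2.1 states: "The primary objective is to provide extended follow-up for safety and efficacy and to support continued islet graft function to participants previously enrolled". Section 7.1 confirms eligibility from the last parent visit and adds no function test.

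**What is analysed.** Section 10.1.1 says "The primary endpoint is time to islet graft failure" and that the analysis will "estimate the probability of islet graft failure as a function of time from entry into the study", by life-table methods. Section 4.1.1 words the endpoint as duration of sustained function, judged by C-peptide at each anniversary of the final transplant.

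**Failures before enrolment.** Section 7.2 provides a retrospective chart review for subjects who enrol late after leaving the parent study, and that review collects evidence of graft failure.

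**The concern.** Eligibility is something the protocol itself has to fix, and here two sections fix it differently. The subjects in dispute can exist. CIT05 section 5.7.2 keeps subjects whose graft has failed in that study until normal termination, so they remain parent-study participants. They can satisfy section 3 of CIT08 and still fall outside section 4. The section 7.2 chart review may also find a failure that happened before a delayed enrolment, in a subject whom section 4 would leave out.

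Because the primary analysis is time to graft failure, the population decides what the curve estimates. Restricted to functioning grafts, it is conditional survival from entry and omits every loss before entry. With all eligible participants, it contains subjects whose event came before time zero, and no rule says how they count. Sites could enrol different populations, and a reader could not tell which quantity the headline figure is.

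**Working it through.** The protocol gives no figure to reproduce: CIT08 expects about 75 subjects and states no sample-size derivation. The check is therefore a comparison of the text, followed by an illustration.

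**Comparison of the text**

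- Graft failed before entry, section 4 followed: not in the cohort.
- Same subject, sections 3.1 and 3.2 followed: eligible if the other criteria are met.
- Synopsis and section 2.1: no function condition.
- The synopsis and section 7.2 make graft-function assessment conditional on its being applicable. That could refer to failures during CIT08, so it does not settle who may enter.
- Section 10.1.1: clock starts at CIT08 entry. Section 4.1.1: anniversaries of the final transplant. Nowhere does CIT08 mention delayed entry.

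**Illustration on the section 10.1.1 clock (time from entry)**

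Inputs: N = 75 (CIT08 section 1.1). The hazard is taken from CIT05 section 1.5.4, which cites C-peptide production in up to 80% of recipients after 5 years. Treating this as a constant hazard that applies after entry is an assumption. The share f failed before entry is also an assumption, because the documents do not give it.

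- Hazard: h = −ln(0.80)/5 = 0.0446 per year.
- Functioning-only curve at 4 years: exp(−4h) = 0.80^(4/5) = 0.837.
- All-participant curve, counting grafts already failed as failures at time zero: (1 − f) × 0.837.

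| Assumed f | Failed at entry, of 75 | Curve at time 0 | All participants, 4 years | Functioning only, 4 years |
|---|---|---|---|---|
| 5% | 4 | 0.947 | 0.792 | 0.837 |
| 10% | 8 | 0.893 | 0.747 | 0.837 |
| 20% | 15 | 0.800 | 0.669 | 0.837 |

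The ratio of the two curves is 1 − f whatever the hazard. The absolute gap at time t is f times the functioning-only survival at t. For scale, the binomial standard error at 0.837 with 75 subjects is √(0.837 × 0.163/75) = 0.043.

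**Illustration on the section 4.1.1 clock (time from final transplant)**

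With the same hazard, survival at years 1, 2 and 3 is 0.956, 0.915 and 0.875. A cohort made up only of grafts functioning at entry in those years, timed from transplant without delayed entry, would show 0.80/0.956 = 0.837, 0.80/0.915 = 0.875 and 0.80/0.875 = 0.915 at year 5, where the assumed survival is 0.80.

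**The case against.** The strongest reply is that survival from entry among functioning grafts is exactly what CIT08 sets out to estimate. Section 1.3 describes follow-up after the parent study is completed, and section 1.4.3 gives the benefit as knowledge of graft function past the parent follow-up period. Earlier losses belong to the parent studies. A life table from entry ordinarily puts only event-free subjects at risk, and the details of a risk set can be left to a statistical analysis plan. CIT08 is also descriptive, with no hypothesis test or stopping rule.

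Most of this stands. It shows that the functioning-only quantity is legitimate, and the fix adopts it. It does not remove the conflict over who may be enrolled, and it does not reconcile the two clocks.

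A reader might also infer three stronger things that the documents do not support.

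- *That the planned curve has guaranteed survival built in.* Section 10.1.1 times it from entry, so it does not. The problem would arise only on the transplant-anniversary clock of section 4.1.1, and that wording can also be read as a visit schedule.
- *That 5-year survival is overstated by 12 or 20 points.* Such gaps need an assumed extra year-1 loss of 10% or 20% on top of the 80% figure. That figure is an upper-end one for recipients overall and is not stated to exclude early losses.
- *That parent-study failure dates can simply be merged in.* CIT05 section 5.7.2 defines failure as undetectable C-peptide, whereas the CIT08 Study Definitions use a level below 0.3 ng/mL. The definitions in the other parent studies are not given in the document.

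**Conclusion.** The contradiction holds, and nothing in CIT08 resolves it. Section 4 requires continuing graft function; sections 3.1 and 3.2, the synopsis and the objective do not. Depending on the section followed, the primary curve starts at 100% and describes survival given function at entry, or includes grafts already failed at time zero without a counting rule. The two time references add to the ambiguity.

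The size cannot be computed from the documents. Under the stated assumptions, the gap in 4-year survival from entry is about 4.5, 9 or 17 percentage points for 5%, 10% or 20% failed before entry. At 10% or more it exceeds the illustrative standard error of about 4 points. These figures rest on a constant hazard from an upper-end 80% at 5 years, on an assumed f, and on counting failed grafts as failures at time zero. They show sensitivity to the population and do not estimate bias in the planned result. This should be corrected, but it does not make the follow-up study unsound.

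**What to change.** 1. State one population in sections 3.1 and 4 and align the synopsis with it. All eligible transplanted parent-study participants may be followed for safety.
2. In section 10.1.1, define the primary risk set as grafts functioning at CIT08 entry, using the protocol's own criterion of C-peptide at or above 0.3 ng/mL. Label the result as graft survival given function at entry.
3. Reconcile sections 4.1.1 and 10.1.1 on one time origin. State which date counts as entry for a late enroller whose gap is filled by chart review. If the origin is the final transplant, use delayed entry (left truncation), so that each subject joins the risk set at CIT08 entry.
4. If survival of all transplanted grafts is also reported, re-derive the parent-study failure dates from parent C-peptide data under the CIT08 definition of below 0.3 ng/mL.

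Items 1 to 3 are wording changes. The C-peptide needed at entry is already scheduled: CIT08 Appendix 1 takes it at screening or from the final parent visit. Item 4 needs some re-derivation work. The other cost is a survival figure that is more narrowly labelled or, for all transplanted grafts, possibly less favourable.
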